#### 4.4 Tertiary endpoints

Tertiary endpoints of this study are:

- Proportion of subjects with Scalp IGA “clear” or “almost clear” with at least two-grade reduction from baseline at Weeks [REDACTED] and 52 among subjects with a baseline Scalp IGA score of  $\geq 3$
- Proportion of subjects with nail psoriasis (baseline mNAPSI score of  $\geq 20$ ) who achieve at least a 75% improvement from baseline in total fingernail mNAPSI at Weeks [REDACTED] and 52
- Proportion of psoriatic arthritis subjects who achieve ACR20 response at Weeks [REDACTED] and 52
- Proportion of subjects with PPPGA score of 0 or 1 at Weeks [REDACTED] and 52 among subjects with a baseline PPPGA score of  $\geq 3$

#### 4.5 Exploratory endpoints

Exploratory endpoints include:

- [REDACTED]
- [REDACTED]
- [REDACTED]
- Proportion of subjects achieving  $\geq$  4-point improvement in Itch Numeric Rating Scale (NRS) from baseline at Weeks [REDACTED], and 52 among subjects with a baseline Itch NRS of  $\geq$  4
- Proportion of subjects achieving  $\geq$  4-point improvement in Scalp Itch NRS from baseline at Weeks [REDACTED] and 52 among subjects with a baseline Scalp Itch NRS of  $\geq$  4
- Change from baseline in subject global assessment of PtA-P at Weeks [REDACTED] and 52 among subjects with PsA at baseline
- [REDACTED]

## 5. ANALYSIS POPULATIONS

### 5.1 Safety Population

The Safety Population will consist of all subjects who were randomized into the study and dispensed study drug. This population will be the primary population for the safety analysis. Subjects will be analyzed according to the actual treatment received.

### 5.2 Intent-to-Treat (ITT) Population

The Intent-to-Treat (ITT) Population will consist of all randomized subjects regardless of whether they received the investigational product. This population will be the main population for the efficacy analyses. Subjects will be analyzed according to the treatment they were randomized to receive.

### 5.3 Per-Protocol (PP) Population

The Per-Protocol (PP) Population will consist of all ITT subjects who meet all inclusion/exclusion criteria, complete Part I of the study and have no protocol violations that affect proper administration of the treatment or accurate evaluation of its effectiveness. For more information on protocol violations see section 6.6. This population will be the supportive population for the efficacy analyses. Subjects will be analyzed according to the treatment they were randomized to receive.

## 6. STATISTICAL METHODS OF ANALYSIS

### 6.1 General Principles

The statistical analyses will be performed using SAS® Version 9.4 (or higher). All tables, figures and listings will be produced in landscape format.

In general, all data will be listed by subject and visit/time point where appropriate. The summary tables will be stratified by, or have columns corresponding to, treatment groups (see section 6.1.1).

The total number of subjects in the treatment group (N) under the specified population will be displayed in the header of summary tables.

Data will be summarized using descriptive statistics for continuous variables. Unless otherwise specified, descriptive statistics will include number of subjects, mean, standard deviation, minimum, median, and maximum. Number of subjects with missing values will also be displayed, but only if non-zero. The minimum and maximum statistics will be presented to the same number of decimal places as the original data. The mean and median will be presented to one more decimal place than the original data. The standard deviation will be presented to two more decimal places than the original data.

In summary tables of categorical variables, counts and percentages will be displayed. The count [n] indicates the actual number of subjects in a particular category, which should always be less than or equal to the total number of subjects in the respective study group with known (non-missing) category [M]. Percentage will be obtained by:  $\% = n/M*100$ . Unless otherwise specified, all percentages will be expressed to one decimal place.

All statistical tests will be two-sided at a significance level of  $\alpha = 0.05$ , unless otherwise indicated.

Baselines will be defined separately for Part I and Part II.

- Part I Baseline is defined as the last assessment, scheduled or not, prior to the first dose of the study drug of the study drug in Part I, unless otherwise specified.
- Part II Baseline is defined as the last assessment, scheduled or not, prior to the first dose of the study drug in Part II. Part II baseline will be used in analysis of findings collected in Parts II, III and IV for subjects who were re-randomized in Part II to another treatment (i.e. SCD-044 [ ] or [ ] after being treated with Placebo in Part I or to SCD-044 [ ] after being treated with SCD-044 [ ] or [ ] in Part I). Throughout this SAP, if the word “baseline” is used without qualification “Part I” or “Part II”, it will refer to Part I baseline.

In by-visit summaries, only data collected on scheduled visits/timepoints will be summarized. Data from unscheduled assessments will be included in listings and may be used in determination of baseline if applicable.

Relative days will be calculated relative to date of first dose of the study drug. Relative days will be calculated as follows only when the full assessment date is known (i.e., partial dates will have missing relative days).

For assessment on or after the day of first dose of the study drug:

Relative Day = Date of Assessment – Date of First Dose of Study Drug+1.

For assessment before the day of first dose of the study drug:

Relative Day = Date of Assessment – Date of First Dose of Study Drug.

All dates will be displayed in DDMMYY format.

### **6.1.1 Treatment Groups**

Data collected up to Week 16 visit will be analyzed by treatment groups based on the subject’s treatment in Part I of the study:

- Placebo

- SCD-044 [REDACTED]
- SCD-044 [REDACTED]
- SCD-044 [REDACTED]

Efficacy data collected after Week 16 visit (i.e., Parts II-IV), as well as disposition and compliance in Parts II-IV, will be analyzed by treatment groups based on the responder status at the end of Part I (Week 16) (i.e.,  $\geq$  PASI50 or  $<$  PASI50), the subject's treatment in Part I and the subject's treatment in Part II of the study:

- Part I Responders
  - Placebo/SCD-044 [REDACTED]
  - Placebo/SCD-044 [REDACTED]
  - SCD-044 [REDACTED]
  - SCD-044 [REDACTED]
  - SCD-044 [REDACTED]
- Part I Non-Responders
  - Placebo/SCD-044 [REDACTED]
  - Placebo/SCD-044 [REDACTED]
  - SCD-044 [REDACTED]
  - SCD-044 [REDACTED]

Safety data collected after Week 16 visit (i.e., Parts II-IV) will be analyzed by treatment groups based on the subject's treatments in Part I and in Part II:

- Placebo/SCD-044 [REDACTED]
- Placebo/SCD-044 [REDACTED]
- SCD-044 [REDACTED]

Adverse events and concomitant medications will be additionally analyzed for the entire study. Details are provided in the sections 6.11.1 and 6.11.6.

### 6.1.2 Adjustment for multiplicity

No adjustment for multiplicity will be needed for the analysis of the primary and key secondary endpoints due to the step-down testing approach described below in this section. P-values for other endpoints, if calculated, will be presented nominally, without multiplicity adjustment. No inferences will be drawn from these p-values.

[REDACTED]

### **6.1.3 Handling of Withdrawals and Missed Data**

In the primary analysis of the primary and the key secondary endpoint subjects with intercurrent events will be treated as non-responders and other missing values will be imputed using multiple imputation approach. See section 6.8.1 for more details. Last Observation Carried Forward (LOCF) and Active Treatment Worst Case (ATWC) imputations as well as tipping-point analysis will be explored in the sensitivity analyses (see section 6.8.2.2). All other endpoints will be summarized as collected without imputations and without any special handling for the intercurrent events.

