3. STUDY OVERVIEW

Start of the study: in North and Latin America: [REDACTED]

in Europe: [REDACTED]

End of the study: the study is expected to be concluded upon final collection of data for all outcome measures and adverse events, including safety follow up (last participant's last visit).

Subjects in this randomized, double-blind, placebo controlled, parallel-group, multiple-center study will be assigned to treatment with the investigational products or placebo control according to a randomization scheme and titration schedule.

- **Part I:** 16 weeks; Subjects will be randomized to placebo, Low dose [REDACTED] Intermediate dose [REDACTED] [REDACTED] or High dose [REDACTED] of SCD-044 [REDACTED]
[REDACTED]
[REDACTED]
[REDACTED] to assess primary and secondary endpoints at Week 16
- **Part II:** Week 16 to Week 28:
At Week 16, subjects initially randomized to a treatment group will be re-randomized or discontinued from the study based on the PASI response as follows:
 - Subjects initially randomized to placebo with a response of:

[REDACTED] will be re-randomized to Intermediate dose, High dose, [REDACTED]
[REDACTED] respectively
[REDACTED] : will be re-randomized to Intermediate dose or High dose [REDACTED]

[figure not shown]
- Subjects originally randomized to Low dose and Intermediate dose arms with a response of:
[REDACTED] will be switched to High dose [REDACTED],
[REDACTED]
[REDACTED] : will remain on their assigned dosing regimen

- Subjects originally randomized to High dose arm with a response of:
[REDACTED]
[REDACTED] : will remain on their assigned dosing regimen

[REDACTED]
[REDACTED]
[REDACTED]
[REDACTED]
[REDACTED]
[REDACTED].

Re-randomized subjects continuing in the study will stay on their assigned dosing regimen until the end of Part II (Week 28). [REDACTED]
[REDACTED]

- **Part III:** Week 28 to Week 52: Subjects with a response of [REDACTED] at Week 28 will be discontinued from the study. Subjects with a response of [REDACTED] at Week 28 will continue their existing dosing regimen until the end of Part III.

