10. A blood sample(s) will be collected for Hematology, Chemistry, and Coagulation profile (See Section 5.5)
11. A blood sample will be collected for PD biomarkers sample (See Section 6.3)
12. A blood sample will be collected within one hour before dosing for PK testing (See Section 6.2)
13. A blood sample will be collected for C-reactive protein (CRP) – (See Section 5.5)
14. Vital signs (blood pressure, pulse, respiratory rate and oral body temperature) will be documented. Subjects must remain in a seated or supine position for at least 5 minutes before vital signs are obtained. (See Section 5.3)

If Subject eligible to continue the study drug dosing based on PASI response ≥75

15. Independent Safety Assessor review:
 - Safety Lab Alerts
 - [REDACTED]
 - As available
 - i. Lab results
 - ii. Exam results
16. Study drug administration in a clinic before 12 noon (See Section 8.5)
17. The following will be dispensed during Visit 16:
 - The study drug assembled for Visit 16
 - A diary card with instructions and to record the study drug use, health changes and concomitant medication
18. A general safety review before discharge
19. [REDACTED]
[REDACTED]
[REDACTED]

If Subject discontinue from the study drug dosing based on PASI response <75 (the visit is to be reported as End of Treatment)

15. Independent Safety Assessor review:
 - Safety Lab Alerts
 - [REDACTED]
 - As available
 - i. Lab results
 - ii. Exam results
16. The following will be dispensed during Visit 16:
 - a. A diary card with instructions and to record health changes and concomitant medication
17. A general safety review before discharge

Confidential

18. [REDACTED]
[REDACTED]

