10. Vital signs (blood pressure, pulse, respiratory rate and oral body temperature) will be documented. Subjects must remain in a seated or supine position for at least 5 minutes before vital signs are obtained. (See Section 5.3)
11. A blood sample(s) will be collected for Hematology, Lipid Profile, Chemistry, and Coagulation profile (See Section 5.5)
12. A blood sample will be collected for PD biomarkers sample (See Section 6.3)
13. A blood sample will be collected within one hour before dosing for PK testing (See Section 6.2)
14. A blood sample will be collected for C-reactive protein (CRP) – (See Section 5.5)
15. A 12-lead electrocardiogram (ECG) will be performed (See Section 5.12)
16. The occurrence of all AEs & AESIs will be assessed and documented following the procedures in Sections 5.9, 10.1, and 10.3.

17. A query for PML (progressive multifocal leukoencephalopathy) will be performed (See Section 5.10)
18. A query for PRES (Posterior reversible encephalopathy syndrome) will be performed (See Section 5.11)
19. A pulmonary function test will be performed or scheduled with an external expert (See Section 5.6)
20. An ophthalmologic examination including OCT will be performed or scheduled with an external expert (See Section 5.7)
21. Study drug administration in a clinic before 12 noon (See Section 8.5)
22. Independent Safety Assessor review:
 - Safety Lab Alerts
 - 12-lead ECG
 - As available
 - i. Lab results
 - ii. Exam results

The following procedures will be performed prior a subject discharged from a clinic:

23. The following will be dispensed during Visit 19:
 - A diary card with instructions and to record health changes and concomitant medication
24. A general safety review before discharge
25. Visit 20 (Study Day 393 ± 3 Days) will be scheduled and the Subject will be instructed to bring the Subject diary with him or her to this visit.

7.1.13 On-site Visit 20: Follow-up Visit (Week 56 / Day 393 ± 3 Days or 4 weeks after End of Treatment)

The following procedures will be performed at Visit 20:

1. A urine pregnancy test will be conducted for all females of childbearing potential (see Section 5.4)

The following procedures will be performed by an independent safety team:

2. The occurrence of all AEs & AESIs will be assessed and documented following the procedures in Sections 5.9, 10.1, and 10.3.
3. A query for PML (progressive multifocal leukoencephalopathy) will be performed (See Section 5.10)

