#### **6.8.3 Analysis of other endpoints**

All other endpoints will be summarized using the ITT population.

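### Week 52 rates labelled ITT cover only Week 28 responders, Week 16 PASI thresholds follow two different rules, and a protocol-specified model is dropped without being declared

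*SAP*

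**What the plan says.** **Missing data and denominators.** SAP 6.1.3 limits non-responder and multiple imputation to the primary and key secondary endpoints, then adds: "All other endpoints will be summarized as collected without imputations and without any special handling for the intercurrent events". SAP 6.1 defines a percentage as n/M, with n a count "which should always be less than or equal to the total number of subjects in the respective study group with known (non-missing) category". By-visit summaries use scheduled visits only. The same section says "The total number of subjects in the treatment group (N) under the specified population will be displayed in the header of summary tables". SAP 6.8.3 sets the population: "All other endpoints will be summarized using the ITT population". SAP 6.8.3.2 attaches a binomial 95% interval to each binary rate.

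**The Week 28 rule.** Protocol 7.1.9 has a branch headed "If Subject discontinue from the study drug dosing based on PASI response <75 (the visit is to be reported as End of Treatment". Protocol Section 3 says subjects with the (blacked-out) response level "at Week 28 will be discontinued from the study". Their next visit is the follow-up in Protocol 7.1.13, which lists no efficacy assessment. The Early Discontinuation list in 7.1.15 has none either.

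**Week 16.** SAP 6.8.1 makes subjects with the listed intercurrent events non-responders for PASI75 and IGA response, and SAP 6.8.2.1 keeps them in the denominator. PASI50, PASI90 and PASI100 are other secondary endpoints and fall under 6.1.3.

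**Models.** Protocol 9.8 assigns an MMRM to the continuous secondary endpoints and applies it also at Week 16 alone. SAP 6.8.3.1 fits it only to change in PASI up to Week 16 and summarises the rest descriptively. SAP Section 8 declares two changes, expanded intercurrent-event handling and a DLQI 0/1 endpoint, and denies any others.

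**The concern.** A Week 52 percentage printed in an ITT table beside the Week 28 percentage will be read as the course of one group. It is not. The design removes subjects on the outcome itself at Week 28, and the n/M rule then takes them out of the denominator. Apparent response can rise while the number of responders falls. The Week 52 figure for Week 16 non-responders switched to high dose (SAP 4.3) is exposed to the same loss. Week 28 rates precede the stop and still include those who fail it.

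At Week 16, every PASI90 responder is by definition a PASI75 responder. Under the SAP, one subject can be a PASI90 responder and a PASI75 non-responder at the same visit.

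For PSSD, DLQI, BSA and percent change in PASI, the reader gets no adjusted treatment difference although the protocol promised one, and Section 8 tells the reader that nothing was dropped.

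The stakes are supportive and descriptive results. SAP 6.1.2 treats other p-values as nominal, and the protocol calls these models supportive.

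**Working it through.** The plan gives no figure of its own for any of these points. From the documents come about 240 subjects allocated 1:1:1:1, so 240/4 = 60 per arm, and nine post-Week 16 efficacy groups in SAP 6.1.1 (5 responder + 4 non-responder), so at most about 240/9 = 26.7 per group on average. All response and loss rates below are assumptions.

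**1. Week 52, general form.** Let N subjects enter a Part II group, q be the share passing Week 28, d the share of those lost later, and R the Week 52 responders. The assessed number is M = N·q·(1−d).

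- Printed rate = R/M
- Rate over entrants = R/N
- Ratio = 1/(q(1−d))

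| q | d | Ratio |
|---|---|---|
| 0.7 | 0 | 1.43 |
| 0.7 | 0.2 | 1.79 |
| 0.4 | 0.1 | 2.78 |
| 0.2 | 0 | 5.00 |
| 0.2 | 0.2 | 6.25 |

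**2. Week 52, worked example** for a group staying on its treatment: N = 25, 10 pass Week 28 (q = 0.4), 1 is lost later (d = 0.1), M = 9, R = 8.

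- Printed Week 28: 10/25 = 40.0%
- Printed Week 52: 8/9 = 88.9% (95% CI 51.8 to 99.7)
- Week 52 over entrants: 8/25 = 32.0% (14.9 to 53.5)

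Responders fall from 10 to 8 while the printed rate more than doubles. The SAP does not name its binomial interval; the exact one is used here.

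**3. What the printed rate responds to.** Take a group of 60 in which about 80% of those continuing hold PASI75 at Week 52, with no other dropout.

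| Pass Week 28 | Printed n/M | Over entrants n/N |
|---|---|---|
| 30% | 14/18 = 77.8% | 14/60 = 23.3% |
| 50% | 24/30 = 80.0% | 24/60 = 40.0% |
| 70% | 34/42 = 81.0% | 34/60 = 56.7% |

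The printed rate barely moves with the number removed. It measures maintenance among Week 28 responders.

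For groups that switch treatment, SAP 6.8.3.2 measures response from the Part II baseline. For them the ratio describes the denominator only, and the rise-while-falling pattern in step 2 is not claimed.

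**4. Week 16, one arm of 60.** Suppose 6 leave with a listed intercurrent event and have no Week 16 value. Of the other 54, 14 have observed PASI75, 12 of those 14 have PASI90, and 2 of those 12 used prohibited medication.

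- PASI75, primary rule: (14 − 2)/60 = 20.0%
- PASI90, as collected: 12/54 = 22.2%
- PASI90, primary rule: (12 − 2)/60 = 16.7%

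**5. Models.**

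| Endpoint | Protocol 9.8 | SAP 6.8.3.1 |
|---|---|---|
| Percent change in PASI | MMRM | Descriptive |
| PSSD | MMRM | Descriptive |
| DLQI | MMRM | Descriptive |
| BSA | MMRM | Descriptive |
| Change in PASI score | Not the listed PASI endpoint | MMRM to Week 16 |

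Four endpoints × 3 doses = 12 Week 16 contrasts with placebo that are not estimated. The SAP was written to protocol version 4.1, and the legible list of changes for version 4.2 shows none to Section 9.8, so the version gap does not explain the difference.

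**The case against.** **Week 28 removals are reported elsewhere.** SAP 6.2 tabulates non-responders discontinued after Part II, and SAP 6.1.1 puts disposition in the same groups as efficacy. With header N, a careful reader can rebuild the all-entrant rate. That is true, but the printed percentage and its interval still use M, and the label still says ITT.

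**Response among those continuing is a legitimate maintenance summary.** It is, and it should be kept. The factor 1/(q(1−d)) compares two different quantities and is not a measured bias. The fault is the label and the absence of the other quantity.

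**The Week 16 inversion needs two tables and chosen counts.** SAP 6.8.3.2 lists PASI75 with the other thresholds. If it were tabulated as collected at Week 16, the example gives 14/54 = 25.9% and 12/54 = 22.2%, which are properly nested. This stands as far as it goes. It would also leave two Week 16 PASI75 figures, 25.9% and 20.0%, and the protocol lists secondary PASI75 only at other weeks.

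**The switch-to-high-dose endpoint names its own denominator, and the table shells are not visible.** This is fair, but no text exempts it from the n/M rule.

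**Early Discontinuation allows extra procedures.** It does, but by-visit summaries use scheduled visits only, so an extra assessment would not supply a Week 52 value.

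**The model loss is modest.** Change in PASI is close to percent change, and PSSD and DLQI have a single post-baseline Part I visit, so their model reduces to ANCOVA. Both points lower the stakes. Neither makes the Section 8 statement correct.

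**Conclusion.** The concern holds on all three points and should be fixed. The Week 52 binary rates are conditional on passing Week 28. Relative to all who enter a Part II group, they are higher by a factor of 1.43 to 6.25 for assumed q of 20 to 70% and d of 0 to 20%; neither q nor d is in the documents. At Week 16, PASI50/90/100 and PASI75 follow different rules and can contradict each other. Four continuous endpoints lose a protocol-specified model, and the SAP says there are no such changes.

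The Week 28 threshold is legible only in Protocol 7.1.9. It is blacked out in the synopsis and Section 3, and the schedule in Protocol 7.2 is not visible, so the same threshold is assumed throughout.

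The primary and key secondary analyses and their error rate are unaffected. The PASI MMRM and the Kaplan-Meier analyses also ignore intercurrent events, because SAP 6.1.3 covers every other endpoint.

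**What to change.** 1. **Week 52 binary endpoints.** Add rates over all subjects entering each Part II group, counting Week 28 removals and later dropouts as non-responders. Keep the as-observed rates, labelled as among Week 28 responders still assessed, with M printed beside N. State that both sets remain conditional on Week 16 response status and are not randomised dose comparisons.
2. **Week 16 PASI50/90/100.** Apply the primary endpoint's rule: listed intercurrent events count as non-response, and other missing responses are derived from the multiply imputed PASI scores that SAP 6.8.1 already generates.
3. **Continuous endpoints in Part I.** Fit the protocol's model with baseline value, gender and prior biologic therapy. Use MMRM for percent change in PASI and for BSA (Weeks 12 and 16), and the single-time-point Week 16 model (ANCOVA) for PSSD and DLQI. Report differences from placebo with 95% intervals. If restricting the model to change in PASI is intended, declare it in SAP Section 8.

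The cost is SAP wording and a few extra tables from data already collected. The added all-entrant Week 52 percentages will look less favourable than the observed ones. Nothing changes in the primary or key secondary analysis.
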